Note: In case of a suspected false positive QuantiFERON[®]-TB Gold result (e.g., a negative result by the local laboratory and suspicion of sample processing error, both of which must be documented in the source document), a second sample may be sent to the central laboratory and the result of the second test will be used.

16. Has any of the following:
- a. An active, clinically significant, bacterial, parasitic, fungal, mycobacterial (including atypical infection), or viral infection, except for local skin or nail bed infection, within 2 weeks prior to Day 1.
 - b. Any infection requiring intravenous antibiotics within 30 days prior to screening.
 - c. Any infection requiring oral antimicrobial treatment within 2 weeks prior to Day 1.
 - d. A history of more than two episodes of herpes zoster or one or more episodes of disseminated/complicated herpes zoster (complicated: multi-dermatomal, ophthalmic, or CNS involvement or post-herpetic neuralgia) or disseminated herpes simplex.
 - e. Has had a chest radiograph or equivalent chest imaging within 90 days prior to Screening or at Screening that shows an abnormality suggestive of a malignancy of current active infection, including TB, chronic lung disease or a potentially active fungal, viral, or bacterial infection.

- f. Has *C. difficile* or other gastrointestinal infections (e.g., *Salmonella*, *Shigella*, *Yersinia*, *Campylobacter*, *E. coli* 0157, etc.) on stool testing or cytomegalovirus (CMV) colitis suspected on endoscopy within 30 days of Day 1.
17. Has ever had a bone marrow transplant.

Coexisting medical conditions or past medical history:

- 18. Are pregnant, lactating, breastfeeding or planning to become pregnant during the Study or within 7 days after the last dose of Study Drug
- 19. Has known moderate or severe hepatic impairment (e.g., Child-Pugh Class B or C)
- 20. Has clinically significant abnormalities in the results of laboratory evaluations at screening visit as determined by the investigator, including:
 - a. AST, ALT, or alkaline phosphatase $\geq 2x$ the upper limit of normal (ULN)
 - b. Total bilirubin $> 2x$ ULN (unless diagnosis of Gilbert's syndrome)
 - c. Creatinine clearance as calculated by the Cockcroft-Gault formula < 30 mL/min (Refer to [Appendix 2](#))
 - d. Total white blood cell count (WBC) $< 3 \times 10^9/L$
 - e. Absolute neutrophil count $< 1.5 \times 10^9/L$
 - f. Absolute lymphocyte count $< 0.8 \times 10^9/L$
 - g. Hemoglobin < 8 g/dL, or

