 - h. Platelet count $< 100 \times 10^9/L$.
- 21. Has a clinically significant abnormal electrocardiogram (ECG) at screening, including QTcF > 450 msec for males and > 470 msec for females.
- 22. Has unstable or uncontrolled and clinically significant allergic (except for untreated, asymptomatic, seasonal allergies), hematological, endocrine/metabolic, coagulation, immunologic, pulmonary, cardiovascular, hepatic (except hepatic steatohepatitis), GI (except UC), genitourinary, psychiatric, oncologic or neurological disease or other medical disorder that would compromise subject safety or confound Study safety assessment as determined by the investigator at screening and Day 1. In addition, subjects with a prior history of thrombotic events, including deep vein thromboses (DVT), and those with known inherited conditions that predispose to hypercoagulability should be excluded.
- 23. Has known hypersensitivity to excipients or contents of the Study drug
- 24. Has participated in another clinical trial of an investigational drug (or medical device) within 30 days prior to Screening or $5x$ the half-life of the investigational drug, whichever is longer, or is currently participating in another trial of an investigational drug (or medical device).
- 25. Have or has a history of alcohol or drug abuse within 1 year of screening, per the judgment of the investigator.
- 26. Has a current, or history of, malignancy requiring radiation or pharmacologic treatment within 5 years prior to screening, except for completely resected basal cell

carcinoma or squamous cell carcinoma of the skin without recurrence for ≥ 1 year, cervical carcinoma in situ that has been adequately treated and without recurrence for ≥ 5 years. Subjects with a history of cervical dysplasia within 3 years prior to screening or who currently have unresected cervical dysplasia should be excluded.

27. Is deemed by the investigator to be inappropriate for this Study; or has any condition which would confound or interfere with the evaluation of the safety, tolerability, or PK of the investigational drug; or is unable or unwilling to comply with the Study protocol.

Exclusion Criteria for Phase 3 Maintenance Study

28. Subjects who required change of UC medications (such as initiated or increased oral corticosteroid dose or initiated rectal aminosalicylates or corticosteroids) or any prohibited medication to control UC symptoms during Induction Study

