3.7.3. Additional Safety Assessments

3.7.3.1. Clinical Laboratory Parameters

Laboratory data, hematology, serum chemistry and urinalysis, will be summarized in terms of observed values and changes from baseline for induction period and overall. In addition, changes from baseline relative to normal ranges from the central lab (e.g., shifts from normal to abnormal high/low) will be summarized.

Summaries for laboratory parameters of special interest will also be presented, these will include:

- Neutrophils
- Leukoocytes
- Lymphocytes
- Hemoglobin
- Lipids [LDL cholesterol, HDL cholesterol, Cholesterol, and Triglyceride]
- Liver Function Test's [ALT, AST, Bilirubin]
- Creatinine
- Creatinine Kinase

The number and percentage of subjects with clinically abnormal lab values will also be summarized by timepoint for the following criteria:

- absolute neutrophil count of $< 1.0 \times 10^9/L$
- white blood cell count of $< 2.0 \times 10^9/L$
- absolute lymphocyte count of $< 0.5 \times 10^9/L$

A summary of maximum National Cancer Institute Common Terminology Criteria for Adverse Events (NCI-CTCAE) toxicity grade (Appendix 5.8) for postbaseline laboratory values through Week 8 and through Week 16.

Listings will flag laboratory values that are outside of normal range.

A listing of all abnormal lab values will be provided. Listings of subjects with any abnormal postbaseline laboratory values of CTCAE grade ≥ 2 will also be provided.

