5.8. CTCAE Grading

Grading Criteria for Clinical Laboratory Tests [CTCAE Version 5.0]					
Hematology Tests		Criteria			
Test	Direction	1	2	3	4
Hemoglobin (g/L)	Decrease	≥ 100 - <LLN	≥ 80 - <100.0	≥ 65 - <80	<65
Leukocytes (WBC) ($10^9/L$)	Decrease	≥ 3.0 - <LLN	≥ 2.0 - <3.0	≥ 1.0 - <2.0	<1.0
Lymphocytes ($10^9/L$)	Decrease	≥ 0.8 - <LLN	≥ 0.5 - <0.8	≥ 0.2 - <0.5	<0.2
Neutrophils ($10^9/L$)	Decrease	≥ 1.5 - <LLN	≥ 1.0 - <1.5	≥ 0.5 - <1.0	<0.5
Platelets ($10^9/L$)	Decrease	≥ 75.0 - <LLN	≥ 50.0 - <75.0	≥ 25.0 - <50.0	<25.0
Chemistry Tests		Criteria			
Test	Direction	1	2	3	4
ALT	Increase	>ULN - ≤ 3.0 Xuan if baseline was normal; 1.5 - 3.0 x baseline if baseline was abnormal	>3.0 xULN - ≤ 5.0 xULN if baseline was normal; >3.0 - 5.0 x baseline if baseline was abnormal	>5.0 xULN - ≤ 20.0 xULN if baseline was normal; >5.0 - 20.0 x baseline if baseline was abnormal	>20.0 xULN if baseline was normal; >20.0 x baseline if baseline was abnormal
Albumin (g/L)	Decrease	≥ 30 - <LLN	≥ 20 - <30	<20	
Alkaline Phosphatase	Increase	>ULN - ≤ 2.5 xULN if baseline was normal; 2.0 - 2.5 x baseline if baseline was abnormal	>2.5 xULN - ≤ 5.0 xULN if baseline was normal; >2.5 - 5.0 x baseline if baseline was abnormal	>5.0 xULN - ≤ 20.0 xULN if baseline was normal; >5.0 - 20.0 x baseline if baseline was abnormal	>20.0 xULN if baseline was normal; >20.0 x baseline if baseline was abnormal
AST	Increase	>ULN - ≤ 3.0 xULN if baseline was normal; 1.5 - 3.0 x baseline if baseline was abnormal	>3.0 xULN - ≤ 5.0 xULN if baseline was normal; >3.0 - 5.0 x baseline if baseline was abnormal	>5.0 xULN - ≤ 20.0 xULN if baseline was normal; >5.0 - 20.0 x baseline if baseline was abnormal	>20.0 xULN if baseline was normal; >20.0 x baseline if baseline was abnormal
Bilirubin	Increase	>ULN - ≤ 1.5 xULN if baseline was normal; > 1.0 - 1.5 x baseline if baseline was abnormal	>1.5 xULN - ≤ 3.0 xULN if baseline was normal; >1.5 - 3.0 x baseline if baseline was abnormal	>3.0 xULN - ≤ 10.0 xULN if baseline was normal; >3.0 - 10.0 x baseline if baseline was abnormal	>10.0 xULN if baseline was normal; >10.0 x baseline if baseline was abnormal
Calcium (mmol/L)	Increase	>ULN - ≤ 2.9	>2.9 - ≤ 3.1	>3.1 - ≤ 3.4	>3.4

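### The Phase 2b SAP specifies its CTCAE laboratory summary without baseline grade, so haemoglobin already at grade 2 on entry is counted with haemoglobin that fell to grade 2 on treatment

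*SAP*

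**What the plan says.** Phase 2b SAP 3.7.3.1 provides for a summary of the maximum NCI-CTCAE "toxicity grade (Appendix 5.8) for postbaseline laboratory values through Week 8 and through Week 16". It adds: "Listings of subjects with any abnormal postbaseline laboratory values of CTCAE grade ≥ 2 will also be provided". Both select on post-baseline values alone. The section names no baseline grade, grade shift or worsening condition.

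Appendix 5.8 of the same SAP treats tests differently. ALT, AST, alkaline phosphatase, bilirubin and GGT have a separate scale when baseline is abnormal; for ALT grade 1, for example, it is "1.5 - 3.0 x baseline if baseline was abnormal". Haemoglobin is graded on absolute limits only: grade 2 is 80 to <100 g/L and grade 3 is 65 to <80 g/L.

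Protocol 4.2, exclusion 20g, sets the only numeric haemoglobin limit at entry: "Hemoglobin < 8 g/dL, or". Exclusion 20 as a whole concerns "clinically significant abnormalities in the results of laboratory evaluations at screening visit as determined by the investigator", and exclusion 22 removes uncontrolled disease, including haematological disease, that "would compromise subject safety or confound Study safety assessment as determined by the investigator".

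Other laboratory outputs in 3.7.3.1 are observed values and changes from baseline, special-interest summaries that include haemoglobin, and the following: "changes from baseline relative to normal ranges from the central lab (e.g., shifts from normal to abnormal high/low) will be summarized". There are also threshold counts ("The number and percentage of subjects with clinically abnormal lab values will also be summarized by timepoint for the following criteria"), and the three criteria listed there are for neutrophils, white cells and lymphocytes.

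**The concern.** The purpose of a post-baseline toxicity table is to show what happened on treatment. For a test graded on fixed limits, a maximum post-baseline grade shows that only if subjects enter below the grade being counted. Haemoglobin does not meet that condition at grade 2: the eligible range contains the whole grade 2 band.

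Protocol 1.5 names decreased red cells among the effects seen with tofacitinib and expects these risks to be minimal for TD-1473, because systemic exposure is low. A count of subjects whose haemoglobin grade worsened would test that expectation directly. As specified, the grade 2 row adds that count to the number who simply arrived with anaemia, and a reader cannot separate the two from the table. What is at stake is the clarity of one descriptive safety display. No efficacy result or error rate depends on it.

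**Working it through.** The plan states no figure on this point, so there is none to reproduce. The check is a comparison of limits, followed by an illustration.

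**1. Entry limits against CTCAE grades.** Entry limits are from Protocol 4.2, exclusion 20, and apply at screening. Grades are from SAP Appendix 5.8.

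| Test | Excluded if | Grade 2 band | Can grade 2 enrol? |
|---|---|---|---|
| Haemoglobin | <8 g/dL = <80 g/L | 80 to <100 g/L | Yes, the whole band |
| White cells (10⁹/L) | <3 | 2.0 to <3.0 | No |
| Neutrophils (10⁹/L) | <1.5 | 1.0 to <1.5 | No |
| Lymphocytes (10⁹/L) | <0.8 | 0.5 to <0.8 | No |
| Platelets (10⁹/L) | <100 | 50 to <75 | No |

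Haemoglobin of grade 3 or worse (<80 g/L) is also barred at screening, so post-baseline grade 3 would normally be worsening. Among the haematology tests, the mixing is confined to haemoglobin grade 2.

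**2. Do other outputs count grade worsening?** Mean change from baseline does not count subjects. The normal-range shift shows grade 1 to 2, stable grade 2, and grade 2 to 3 all as low to low. The threshold counts leave haemoglobin out. The content of the special-interest summaries is not described. Listings hold the values but leave the counting to the reader.

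**3. Size, as an illustration.** The documents give neither the share entering at grade 2 nor any emergent rate, so every rate below is assumed. Only n = 60 per arm comes from the plan (SAP 1.5). Let b be the share entering at grade 2, s the share of those still at grade ≥2 at their worst post-baseline value (the same in both arms), and e the emergent grade ≥2 rate in the rest. No carried-in subject worsens to grade 3.

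- Expected count as planned: 60 × [b·s + (1−b)·e]
- Expected count worsened to grade ≥2: 60 × (1−b)·e

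For b = 10%, s = 1 and e = 2% versus 10%, the planned counts are 60 × (0.10 + 0.90 × 0.02) = 7.1 and 60 × (0.10 + 0.90 × 0.10) = 11.4. The worsened-only counts are 60 × 0.018 = 1.1 and 60 × 0.09 = 5.4. Other values of b, with s = 1:

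| b | Planned, placebo vs drug (ratio) | Worsened to grade ≥2 (ratio) | Difference, both ways | Carried-in share of planned drug-arm count |
|---|---|---|---|---|
| 2% | 2.4 vs 7.1 (2.98) | 1.2 vs 5.9 (5.0) | 4.7 | 17% |
| 5% | 4.1 vs 8.7 (2.10) | 1.1 vs 5.7 (5.0) | 4.6 | 34% |
| 10% | 7.1 vs 11.4 (1.61) | 1.1 vs 5.4 (5.0) | 4.3 | 53% |
| 15% | 10.0 vs 14.1 (1.41) | 1.0 vs 5.1 (5.0) | 4.1 | 64% |

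The term b·s cancels in the difference, so the difference is the same either way. What changes is the ratio and the noise. With SE = √[p₀(1−p₀)/60 + p₁(1−p₁)/60], difference/SE at b = 10% is 1.10 as planned (p = 0.118 and 0.190) and 1.77 for worsening only (p = 0.018 and 0.090).

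Sensitivity at b = 10%:

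- Half of the carried-in subjects improve (s = 0.5): planned ratio 2.06.
- Emergent rates 5% versus 10%, s = 1: ratio 1.31 as planned, 2.0 for worsening only.
- Emergent rates 2% versus 5%, s = 1: ratio 1.23 as planned, 2.5 for worsening only.

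These figures are for worsening to grade ≥2. They do not describe a count of any worsening, which would include grade 0 to 1.

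**The case against.** The strongest reply is that the SAP is silent on layout rather than opposed to baseline grade. Table shells are not part of the documents, and they may already cross-classify. The special-interest haemoglobin summary could also carry a change criterion, since Protocol 8.8.4 speaks of both values and changes of special interest. This stands as a limit on certainty. It does not remove the point: the rule as written counts maximum post-baseline grade, and a table programmed literally from it would mix the two groups.

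A second reply is that worsening is captured elsewhere. Protocol 7.1.1 counts clinically significant laboratory changes from baseline as AEs, and Protocol 6.4.1.3 records conditions that worsen after the first dose as treatment-emergent. Clinically significant worsening of haemoglobin should therefore reach the TEAE tables. This also stands, in part. Under Protocol 7.2 a laboratory change becomes an AE only with signs or symptoms or on the investigator's judgement, and Protocol 7.3.1 scores severity by effect on routine activity. The TEAE tables do not count laboratory grades.

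Third, investigators may exclude clinically significant anaemia under exclusions 20 and 22. That may lower the share entering at grade 2, but no numeric rule keeps it at zero.

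A reader might go further and infer that the table biases the comparison of drug with placebo, or that the whole CTCAE table is unreliable. The documents support neither. Randomisation gives the arms the same expected background, and the entry limits protect the grade ≥2 rows for white cells, neutrophils, lymphocytes and platelets.

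**Conclusion.** The point holds in a narrow form. The specified CTCAE summary and grade ≥2 listing do not refer to baseline grade; haemoglobin grade 2 can be present at entry; and no named output counts subjects whose grade worsened. The consequence is dilution of a descriptive contrast in the haemoglobin grade 2 cell, not bias and not an inferential error.

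How much dilution there is cannot be estimated from the documents. In the illustration the planned ratio falls from 2.98 to 1.41 as the assumed carried-in share rises from 2% to 15%, against 5.0 for worsening only. Exact cancellation in the difference rests on the same share staying at grade 2 in each arm. No between-arm ratio or test is planned for laboratory grades, so the effect is on how clearly the table reads. Confidence is high that the SAP text names no grade shift; it does not extend to the final table layout.

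**What to change.** In Phase 2b SAP 3.7.3.1:

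- Present maximum post-baseline CTCAE grade by baseline grade, through Week 8 and through Week 16.
- Add the number and percentage of subjects whose grade worsened from baseline to grade ≥2, and show any worsening separately.
- For a missing baseline, apply the existing rule in 5.2.3 (last available assessment, generally screening) rather than assuming grade 0.
- Flag worsened grade in the grade ≥2 listing.

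If the table shells already do this, one sentence in the SAP saying so is enough. The same change in the Maintenance SAP is optional, because that study was terminated early. The cost is a small change of SAP wording, one reprogrammed descriptive table and a listing flag. The laboratory values are already collected, and grading is already planned.

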3.7.3.2. Vital Signs

Descriptive statistics for vital signs (systolic and diastolic blood pressures, pulse rate, and weight) and changes from baseline values at each visit and at the end of study will be presented by treatment group.

For each nominal time point, vital signs will be summarized in terms of observed values and changes from baseline. Marked abnormalities as defined in Table 9 will be flagged in the listing.

Table 9: Criteria for Marked Abnormalities in Vital Signs

Heart Rate (bpm)	Systolic Blood Pressure (mm Hg)	Diastolic Blood Pressure (mm Hg)
< 40	< 85	< 45
> 110	> 160	> 100

3.7.3.3. Electrocardiograms

Descriptive statistics for ECG parameters (heart rate, RR interval, PR interval, QRS interval, QT interval, and QTcF) and changes from baseline values at each assessment time point to the end of study will be presented by treatment group. The QTcF will be calculated using the Fridericia correction.

Subjects without a postbaseline measurement for a given treatment period will be excluded from the summary statistics (e.g., denominator of the summary statistic) for that time point.

All recorded values for the standard 12-lead electrocardiogram parameters will be presented in a by-subject listing.

Categorical Analyses

The number (percentage) of subjects with absolute ECG values and change from baseline in the ranges shown in Table 10 will be presented in Electrocardiogram Categorical Summary by Visit and Time Point.

In addition, in the same summary, QTcF will also be summarized by the following categories, Normal (males < 430, females ≤ 450), Borderline (males (> 430, ≤ 450); females (> 450, ≤ 470)) and Prolonged (males > 450, females > 470).

Individual ECG data collected during the study will be presented in a listing. A separate listing of subjects with values of QTcF > 500 msec or an increase > 60 msec will be provided, as necessary.

Investigator Assessment of ECG Readings

The investigators’ assessment of ECGs as normal, abnormal and clinically significant, or abnormal but not clinically significant will be summarized for baseline and for each visit.

Table 10: ECG Interval Categories

Heart Rate (bpm)	Heart Rate Change from Baseline (bpm)	PR Interval (msec)	PR Percentage Change From Baseline (%)	QRS Interval (msec)	QT _c F (msec)	QT _c F change from Baseline (msec)
> 120	≥ 20	≥ 200	≥ 15	≥ 120	Males:	≤ 30
> 130	≥ 30	≥ 220	≥ 25		< 430	>30, ≤ 60
					≥ 430	> 60

[REDACTED]

[REDACTED]

[REDACTED]

[REDACTED]

[REDACTED]

[REDACTED]

[REDACTED]

[REDACTED]

[REDACTED]

[REDACTED]

[REDACTED]

[REDACTED]

[REDACTED]

[REDACTED]

[REDACTED]

[REDACTED]

[REDACTED]

[REDACTED]

3.9. Interim Analyses

The study will have an interim freeze to perform the primary analysis after the last subject ongoing in induction period reaches the Week 8b/mWk0 timepoint or discontinues.

3.9.1. Maintenance of blind following interim analysis

Study team members with access to subject level data during the interim analysis that reveals a subjects dose (i.e. 20mg, 80mg or 200mg) during the Extended Induction period cannot participate in study-related activities that involve direct site interaction from Week 8 unblinding onwards.

3.9.2. Data Monitoring Committee

[REDACTED]

5. SUPPORTING DOCUMENTATION

5.1. Appendix 1: Changes to Protocol-Planned Analyses

The endpoints and analysis have been updated follow the advice in ICH E9 (R1) addendum on estimands and sensitivity analysis in clinical trials to the guideline on statistical principles for clinical trials. As a result, endpoints following a treatment policy strategy no longer omit data meeting treatment failure criteria as outlined in the protocol section 8.9.

5.2. Appendix 2: Data Conventions and Transformations

5.2.1. Derived and Transformed Data

5.2.1.1. Study Day

If the date of interest occurs on or after the first dose/randomization date then study day will be calculated as (date of interest – date of first dose/randomization) + 1.

If the date of interest occurs prior to the first dose/randomization date then study day will be calculated as (date of interest – date of first dose/randomization).

There is no Study Day 0.

5.2.1.2. Change from baseline

Change from baseline is calculated as (postbaseline result – baseline result).

Percent change from baseline is calculated as ((change from baseline/baseline result) × 100) or equivalently as 100(postbaseline value/baseline value - 1).

If either the baseline or the postbaseline result is missing, the change from baseline and percentage change from baseline values are missing.

5.2.1.3. BMI

BMI is calculated as:

$$BMI (kg / m^2) = \frac{weight (kg)}{height (m)^2}.$$

5.2.1.4. Ideal Body Weight

Ideal body weight is calculated as follows (Devine 1974):

- 50 kg + 2.3 kg for each 2.54 cm (1 in) over 152.4 cm (5 ft), if male
- 45.5 kg + 2.3 kg for each 2.54 cm (1 in) over 152.4 cm (5 ft), if female

This is a conversion to metric units of the following simple rule:

- For women, allow 100 lb for the first 5 feet and 5 lb for each additional inch.

- For men, allow 110 lb for the first 5 feet and 5 lb for each additional inch.

5.2.1.5. QTcF

QTcF is calculated as:

$$QTcF = \frac{QT}{\left(\frac{RR}{1sec}\right)^{\frac{1}{3}}}$$

5.2.1.6. Time Since Ulcerative Colitis Diagnosis

Time since UC diagnosis (years) as of the first dose date is calculated as (first dose date - diagnosis date)/365.25. It is left unrounded for calculation of summary statistics but rounded to 1 decimal place for display.

5.2.1.7. Prior Biologic Failure

Subjects who have entered primary non-response, secondary non-response or intolerant to at least one biologic treatment are defined as failing prior biologic treatment. All other subjects regardless of receiving prior biologic treatment are not considered failures.

Subjects who have not received a biologic are considered “biologic-naïve”.

Subjects who have received a biologic but have not met the criteria for failure above are considered “bio-experienced [but not documented failure]”.

